5.3.5.10 Hospitalization or Prolonged Hospitalization

Any adverse event that results in hospitalization (i.e., inpatient admission to a hospital) or prolonged hospitalization should be documented and reported as a serious adverse event (per the definition of serious adverse event in Section 5.2.2), except as outlined below.

An event that leads to hospitalization under the following circumstances should not be reported as an adverse event or a serious adverse event:

- Hospitalization for respite care
- Hospitalization for a preexisting condition, provided that all of the following criteria are met:

The hospitalization was planned prior to the study or was scheduled during the study when elective surgery became necessary because of the expected normal progression of the disease

The patient has not experienced an adverse event

An event that leads to hospitalization under the following circumstances is not considered to be a serious adverse event, but should be reported as an adverse event instead:

- Hospitalization that was necessary because of patient requirement for outpatient care outside of normal outpatient clinic operating hours

5.4 IMMEDIATE REPORTING REQUIREMENTS FROM INVESTIGATOR TO SPONSOR

Certain events require immediate reporting to allow the Sponsor to take appropriate measures to address potential new risks in a clinical trial. The investigator must report such events to the Sponsor immediately; under no circumstances should reporting take place more than 24 hours after the investigator learns of the event. The following is a list of events that the investigator must report to the Sponsor within 24 hours after learning of the event, regardless of relationship to study drug:

- Serious adverse events (defined in Section 5.2.2; see Section 5.4 for details on reporting requirements)
- Adverse events of special interest (defined in Section 5.2.3, see Section 5.4.2 for details on reporting requirements)
- Pregnancies (see Section 5.4.3 for details on reporting requirements)

The Sponsor will promptly evaluate all serious adverse events and adverse events of special interest against cumulative product experience to identify and expeditiously communicate possible new safety findings to investigators, IRBs/ECs, drug manufacturers, and health authorities based on applicable legislation.

5.4.2 Reporting Requirements for Serious Adverse Events, Adverse Events of Special Interest

5.4.2.1 Events That Occur prior to Study Treatment Initiation

After informed consent has been obtained but prior to initiation of study treatment, only serious adverse events caused by a protocol-mandated intervention should be reported. The paper Clinical Trial Serious Adverse Event/Adverse Event of Special Interest Reporting Form provided to investigators should be completed and submitted to the Sponsor or its designee immediately (i.e., no more than 24 hours after learning of the event), either by faxing or by scanning and emailing the form using the fax number or email address provided to investigators.

5.4.2.2 Events That Occur after Study Treatment Initiation

After initiation of study treatment, serious adverse events and adverse events of special interest will be reported until 28 days after the final dose of study treatment. Investigators should record all case details that can be gathered immediately (i.e., within 24 hours after learning of the event) on the Adverse Event eCRF and submit the report via the electronic data capture (EDC) system. A report will be generated and sent to Safety Risk Management by the EDC system.

In the event that the EDC system is unavailable, the paper Clinical Trial Serious Adverse Event/Adverse Event of Special Interest Reporting Form provided to investigators should be completed and submitted to the Sponsor or its designee immediately (i.e., no more than 24 hours after learning of the event), either by faxing or by scanning and emailing the form using the fax number or email address provided to investigators. Once the EDC system is available, all information will need to be entered and submitted via the EDC system.

Instructions for reporting serious adverse events that occur >28 days after the final dose of study treatment are provided in Section [5.6](#).

5.4.3 Reporting Requirements for Pregnancies

5.4.3.1 Pregnancies in Female Patients

Female patients of childbearing potential will be instructed through the Informed Consent Form to immediately inform the investigator if they become pregnant during the study or within 28 days after the final dose of azithromycin. A paper Clinical Trial Pregnancy Reporting Form should be completed and submitted to the Sponsor or its designee immediately (i.e., no more than 24 hours after learning of the pregnancy), either by faxing or by scanning and emailing the form using the fax number or email address provided to investigators. Pregnancy should not be recorded on the Adverse Event eCRF. The investigator should discontinue study treatment and counsel the patient, discussing the risks of the pregnancy and the possible effects on the fetus. Monitoring of the patient should continue until conclusion of the pregnancy. Any serious adverse events associated with the pregnancy (e.g., an event in the fetus, an event in the mother during or after the pregnancy, or a congenital anomaly/birth defect in the child) should be reported on the Adverse Event eCRF. In addition, the investigator will submit a paper Clinical Trial Pregnancy Reporting Form when updated information on the course and outcome of the pregnancy becomes available.

5.4.3.2 Abortions

A spontaneous abortion should be classified as a serious adverse event (as the Sponsor considers abortions to be medically significant), recorded on the Adverse Event eCRF, and reported to the Sponsor immediately (i.e., no more than 24 hours after learning of the event; see Section [5.4](#)).

If a therapeutic or elective abortion was performed because of an underlying maternal or embryofetal toxicity, the toxicity should be classified as a serious adverse event, recorded on the Adverse Event eCRF, and reported to the Sponsor immediately (i.e., no more than 24 hours after learning of the event; see Section 5.4). A therapeutic or elective abortion performed for reasons other than an underlying maternal or embryofetal toxicity is not considered an adverse event.

All abortions should be reported as pregnancy outcomes on the paper Clinical Trial Pregnancy Reporting Form.

5.4.3.3 Congenital Anomalies/Birth Defects

Any congenital anomaly/birth defect in a child born to a female patient exposed to study drug or the female partner of a male patient exposed to study drug should be classified as a serious adverse event, recorded on the Adverse Event eCRF, and reported to the Sponsor immediately (i.e., no more than 24 hours after learning of the event; see Section 5.4).

5.5 FOLLOW-UP OF PATIENTS AFTER ADVERSE EVENTS

5.5.1 Investigator Follow-Up

The investigator should follow each adverse event until the event has resolved to baseline grade or better, the event is assessed as stable by the investigator, the patient is lost to follow-up, or the patient withdraws consent. Every effort should be made to follow all serious adverse events considered to be related to study drug or trial-related procedures until a final outcome can be reported.

During the study period, resolution of adverse events (with dates) should be documented on the Adverse Event eCRF and in the patient's medical record to facilitate source data verification.

All pregnancies reported during the study should be followed until pregnancy outcome.

5.5.2 Sponsor Follow-Up

For serious adverse events, adverse events of special interest, and pregnancies, the Sponsor or a designee may follow up by telephone, fax, email, and/or a monitoring visit to obtain additional case details and outcome information (e.g., from hospital discharge summaries, consultant reports, autopsy reports) in order to perform an independent medical assessment of the reported case.

5.6 ADVERSE EVENTS THAT OCCUR AFTER THE ADVERSE EVENT REPORTING PERIOD

The Sponsor should be notified if the investigator becomes aware of any serious adverse event that occurs after the end of the adverse event reporting period (defined as 28 days after the final dose of study drug), if the event is believed to be related to prior study treatment. These events should be reported through use of the Adverse Event

¹²⁹Xe MRI—Genentech, Inc.

66/Protocol GE42063, Version 5

eCRF. However, if the EDC system is not available, the investigator should report these events directly to the Sponsor or its designee, either by faxing or by scanning and emailing the paper Clinical Trial Serious Adverse Event/Adverse Event of Special Interest Reporting Form using the fax number or email address provided to investigators.

5.7 EXPEDITED REPORTING TO HEALTH AUTHORITIES, INVESTIGATORS, INSTITUTIONAL REVIEW BOARDS, AND ETHICS COMMITTEES

The Sponsor will promptly evaluate all serious adverse events and adverse events of special interest against cumulative product experience to identify and expeditiously communicate possible new safety findings to investigators, IRBs, ECs, and applicable health authorities based on applicable legislation.

To determine reporting requirements for single adverse event cases, the Sponsor will assess the expectedness of these events through use of the reference safety information in the documents listed below:

Drug	Document
Azithromycin	Single drug covered by prescribing information: Azithromycin E.U. Summary of Product Characteristics
¹²⁹ Xe MRI	Drug device combination covered by combination Investigator's Brochure: HP ¹²⁹ Xe and MRI Investigator's Brochure

HP = hyperpolarized; MRI = magnetic resonance imaging.

The Sponsor will compare the severity of each event and the cumulative event frequency reported for the study with the severity and frequency reported in the applicable reference document.

Reporting requirements will also be based on the investigator's assessment of causality and seriousness, with allowance for upgrading by the Sponsor as needed.

A SMC will monitor the incidence of the above-listed anticipated events during the study. An aggregate report of any clinically relevant imbalances that do not favor the test product will be submitted to health authorities.

6. STATISTICAL CONSIDERATIONS AND ANALYSIS PLAN

6.1 DETERMINATION OF SAMPLE SIZE

Power calculations for this exploratory study require many assumptions due to lack of available literature on the ¹²⁹Xe MRI metrics. Further details than those provided in the protocol, including code to generate these calculations, are available in the Statistical Analysis Plan (SAP). All calculations were done in R version 3.5.0. The focus of this trial is on estimation, not hypothesis testing.

The main objective of this study is establishing if ^{129}Xe MRI metrics (VDP) are a more sensitive measure of lung function decline and can predict the rate of moderate/severe exacerbation. Approximately 100 patients in Cohort A will be enrolled in this study. A sample size of 100 will enable enough exacerbations to anchor the evaluation of the performance of VDP.

This study is powered (at 77%) to detect a treatment effect due to exacerbation, depending on assumptions. Power calculation was done based on a negative binomial with over-dispersion of 1.3 (COPD BEAT data), with 5% alpha, assuming a mean exacerbation frequency of 2 and observed for 48 weeks. A one-sided test was used and 10% drop-out rate. A further assumption on the azithromycin effect size was needed to establish power—a 35 % reduction rate ratio was used (Seemungal et al. 2008).

This study is powered, depending on assumptions, for the secondary efficacy objectives. To test the sensitivity of VDP metric relative to FEV_1 (coefficient of variation test), a sample size of 100 provides just under 90% power to establish improved coefficient of variation relative to FEV_1 (assumes coefficient of variation observed in Weatherly et al. 2019 of 180% and using a simulation-based power calculation run with MSLR and a p-value of 0.05.)

This study is well powered to test the secondary efficacy objective of establishing the relationship between HRCT metrics and the VDP metric. With a sample size of 100, and assuming a true correlation of 0.25 between the metrics, the study has approximately 75% power to determine if a correlation exists (assuming a multivariate normal with correlation of 0.25 and PRM^{SAD} mean of 26.6% and standard deviation of 11.6% [Bhatt et al. 2016]). Assumptions of operating characteristics of ^{129}Xe MRI metric, VDP, come from Smith et al. 2018 (mean=4.37, SD=1.89).

Exploratory endpoints of RDP and BDP were not evaluated in terms of power. They are purely exploratory and there is no literature on which to base a power calculation.

6.2 SUMMARIES OF CONDUCT OF STUDY

The number of patients who enroll, discontinue, or complete the study will be summarized. Reasons for premature study discontinuation will be listed and summarized. Enrollment and major protocol deviations will be listed and evaluated for their potential effects on the interpretation of study results.

6.3 SUMMARIES OF TREATMENT GROUP COMPARABILITY OR DEMOGRAPHIC AND BASELINE CHARACTERISTICS

Demographic and baseline characteristics (including age, sex, COPD-CB) will be summarized using means, standard deviations, medians, and ranges for continuous variables and proportions for categorical variables, as appropriate. Summaries will be presented overall and by treatment group.

6.4 EFFICACY ANALYSES

The analysis population for the efficacy analyses will consist of all patients, with patients grouped according to their assigned treatment.

6.4.1 Primary Efficacy Endpoints

The primary efficacy endpoints are detailed in Section [2.1.1](#).

Details of the analysis are available in the SAP, including sensitivity analysis. At a minimum, VDP change at 24 weeks can predict rate of moderate/severe COPD exacerbation over 48 weeks, controlling for treatment assignment. The initial model will be a negative binomial model for exacerbation rate using the intent-to-treat (ITT) population. As this is an exploratory study, sensitivity analysis is performed for the purpose of confirming signal. If signal is not found using the primary analysis, sensitivity analysis will not be performed.

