HP xenon (¹²⁹Xe) will be administered at *specified timepoints and the total dose bag volume should target 20% of the patient's forced vital capacity* followed by a breath hold of up to 15 seconds. Subsequent ¹²⁹Xe doses will only be administered once the patient is ready to proceed. Patients will be monitored by a qualified medical professional for the duration of the xenon dose and post-procedural period, as well as the MRI. *Refer to the study imaging manual for details.*

NON-INVESTIGATIONAL MEDICINAL PRODUCTS

Required COPD inhaler therapies, consisting of LABA and/or LAMA with or without ICS therapy, are considered non-IMPs for this study.

STATISTICAL METHODS

PRIMARY ANALYSIS

Details of the analysis are available in the Statistical Analysis Plan, including sensitivity analysis. At a minimum, VDP change at 24 weeks can predict rate of moderate/severe COPD exacerbation over 48 weeks, controlling for treatment assignment. The initial model will be a negative binomial model for exacerbation rate using the intent-to-treat population. As this is an exploratory study, sensitivity analysis is performed for the purpose of confirming signal. If signal is not found using the primary analysis, sensitivity analysis will not be performed.

DETERMINATION OF SAMPLE SIZE

Power calculations for this exploratory study require many assumptions due to lack of available literature on the ¹²⁹Xe MRI metrics. Further details than those provided in the protocol, including code to generate these calculations, are available in the Statistical Analysis Plan. All calculations were done in R version 3.5.0. The focus of this trial is on estimation, not hypothesis testing.

The main objective of this study is establishing if ¹²⁹Xe MRI metrics (VDP) are a more sensitive measure of lung function decline and can predict the rate of moderate/severe exacerbation. Approximately 100 patients in Cohort A will be enrolled in this study. A sample size of 100 will enable enough exacerbations to anchor the evaluation of the performance of VDP.

This study is powered (at 77%) to detect a treatment effect due to exacerbation, depending on assumptions. Power calculation was done based on a negative binomial with over-dispersion

of 1.3, with 5% alpha, assuming a mean exacerbation frequency of 2 and observed for 48 weeks. A one-sided test was used and 10% drop-out rate. A further assumption on the azithromycin effect size was needed to establish power—a 35 % reduction rate ratio was used.

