Magnetic resonance imaging (MRI) using hyperpolarized (HP) xenon-129 gas (¹²⁹Xe) is an emerging technology capable of 3D mapping of ventilation and gas distribution in the alveolar space and its uptake in interstitial barrier tissues (“barrier uptake”), as well as its transfer to red blood cells (Driehuys 2012; Joseph 2019). Recent studies comparing healthy smokers, patients with COPD, and non-smokers support the potential of ¹²⁹Xe MRI to identify multiple physiological lung changes using a single breath-hold (Qing 2019). This allows for discrimination between healthy subjects and healthy smokers prior to loss of lung function assessed by FEV₁ and could become a powerful new measure of early-stage lung disease (Qing et al. 2019; Ruppert 2019). Importantly, this assessment may offer improved sensitivity compared with an AEx endpoint allowing for shorter duration clinical trials.

Few studies have shown any impact of chronic azithromycin treatment on clinically relevant measures of COPD such as FEV₁, or quality of life associated with prophylactic treatment with azithromycin. COPD manifests in a spatially heterogeneous manner, with areas of normal lung in close proximity to areas of small airways disease, fibrosis, and emphysema. Thus, detection of progression and response to therapy requires local assessment of lung structure and function, with the ability to monitor these regions over time. Currently, no single established assessment modality provides a comprehensive regional evaluation of both ventilation and gas exchange. Although high-resolution computed tomography (HRCT) is integral to the diagnosis of COPD/emphysema, it is

¹²⁹Xe MRI—Genentech, Inc.

21/Protocol GE42063, Version 5

poorly suited to monitor therapeutic response. Computed tomography (CT) scans detect structural abnormalities, but the earliest harbinger of changing disease status is lung function. Additionally, CT scans and HRCT scans require use of ionizing radiation. The ability to image both lung function and structure may now be addressed by HP ¹²⁹Xe MRI.

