1.3 STUDY RATIONALE AND BENEFIT-RISK ASSESSMENT

¹²⁹Xe MRI is capable of 3D-mapping ventilation and gas distribution in the alveolar space and its uptake in interstitial barrier tissues (“barrier uptake”), as well as its transfer to red blood cells (“RBC transfer”). Because ¹²⁹Xe, like oxygen, must traverse the interstitial barrier to reach capillary blood, ¹²⁹Xe signal in RBCs is exquisitely sensitive to barrier thickness. ¹²⁹Xe in RBCs has a unique frequency shift, allowing it to reveal interstitial thickening of only a few microns. This high sensitivity to altered blood-gas-barrier in regions of small airways disease and emphysema makes ¹²⁹Xe MRI uniquely suited to study COPD without the use of potentially harmful ionizing radiation. This has the potential to accelerate clinical trials for COPD by visualizing the therapeutic response on the timescale of months versus years.

This study aims to assess whether change from baseline in ¹²⁹Xe MRI metrics for ventilation defect percent (VDP), barrier defect percent (BDP), and/or RBC defect percent (RDP) at 24 weeks can predict rate of exacerbation over a 48-week period, and whether baseline ¹²⁹Xe MRI metrics are prognostic for AEx rate and/or predictive of clinical benefit from daily treatment with azithromycin.

Azithromycin use has been shown to reduce AECOPD, but carries some risk to patients (Taylor et al. 2015). These include a small risk for QT-interval prolongation, hearing loss, and the development of antibacterial resistance. Nonetheless, with adequate safety monitoring (see Section 5.1), reduced risk for recurrent exacerbations may benefit patients’ overall quality of life and long-term outcomes.

An assessment has been conducted to determine whether the coronavirus disease 2019 pandemic has any impact on the benefit-risk assessment of this study including, but not limited to, the patient population under study and study treatments (azithromycin and hyperpolarized ¹²⁹Xe). The safety monitoring and management guidelines and risk mitigation measures provided in the study are considered adequate.

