2.1 EFFICACY OBJECTIVES

2.1.1 Primary Efficacy Objective

The primary efficacy objective for this study is to characterize the relationship between ^{129}Xe MRI metrics and clinical outcome in patients treated with AZM + SOC versus SOC on the basis of the following endpoint:

- Change in ^{129}Xe MRI VDP from baseline to Week 24 compared with rate of moderate or severe COPD exacerbations over 48 weeks

A moderate COPD exacerbation is defined as new or increased COPD symptoms (e.g., dyspnea, sputum volume, and sputum purulence) for at least 2 consecutive days that lead to treatment with systemic corticosteroids and/or antibiotics.

A severe COPD exacerbation is defined as new or increased COPD symptoms (e.g., dyspnea, sputum volume, and sputum purulence) for at least 2 consecutive days that lead to hospitalization or death.

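### Half of the 48-week exacerbation window precedes the Week 24 VDP change said to predict it, so the primary model alone shows association, not prediction of later events

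*Combined protocol and SAP*

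**What the plan says.** Section 2.1.1 sets the change in ¹²⁹Xe "MRI VDP from baseline to Week 24 compared with rate of moderate or severe COPD exacerbations over 48 weeks", under an objective to characterise a relationship. Section 6.4.1 states it as prediction: "At a minimum, VDP change at 24 weeks can predict rate of moderate/severe COPD exacerbation over 48 weeks, controlling for treatment assignment". The model is negative binomial, in the intent-to-treat population. The synopsis has the same wording ("VDP change at 24 weeks can predict rate of moderate/severe COPD exacerbation over 48 weeks"). Section 1.3 asks whether the change in the MRI metrics "at 24 weeks can predict rate of exacerbation over a 48-week period", and Section 6.1 makes it part of the main objective that VDP "can predict the rate of moderate/severe exacerbation". Section 6.1 also says: "The focus of this trial is on estimation, not hypothesis testing".

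Visits end at Week 48, with a telephone call at Week 52 in Cohort A (Section 4.6.2), so the 48 weeks cannot start at the scan. Section 6.4.1 leaves analysis details to the SAP and adds: "If signal is not found using the primary analysis, sensitivity analysis will not be performed". The combined document as supplied holds protocol text only. Nothing in it restricts the primary outcome to events after Week 24 or adjusts for earlier ones. The alternative-timepoint sensitivity analyses in Sections 6.4.2 and 6.4.3 belong to the secondary and exploratory endpoints.

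**The concern.** A predictor should be known before the outcome it predicts. Here the change is complete only at the scan, and events from the preceding 24 weeks count in the outcome. Two errors are possible, in opposite directions.

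- **Carry-over.** If an exacerbation before Week 24 worsens VDP, the early events raise both the predictor and the outcome, and the model cannot tell this from forward prediction. The documents do not say whether this happens. Section 3.3.1 does cite a link between exacerbations and FEV₁ loss. Appendix 1 allows spirometry to be omitted during an acute exacerbation, and the protocol states no such condition for the Week 24 scan (the imaging manual may).
- **Dilution.** If VDP change foretells only later events, the early events add noise and pull the estimate towards no effect.

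At stake is what may be said afterwards: that VDP change is associated with the 48-week rate, or that it foretells exacerbations still to come.

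**Working it through.** The plan states no effect size or power for the VDP-exacerbation relationship, so there is no figure of its own to reproduce. Its 77% power concerns the treatment effect and is not used here.

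**Inputs from the plan** (Section 6.1, Section 3.1, Appendix 1): 100 patients randomised 1:1, 10% dropout, mean frequency 2, 35% reduction, 48 weeks, over-dispersion 1.3, Week 24 and Week 48 visits each within ±7 days. This gives 45 evaluable patients per arm and rates of 2 and 2 × 0.65 = 1.3.

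**Overlap.** 24/48 = 50%. With the visit windows it runs from 23/49 = 47% to 25/47 = 53%.

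**Expected events, constant rate.** With the rate read per 48 weeks: 45 × 2 + 45 × 1.3 = 148.5, of which half, 74, precede the scan. With the rate read per year: 148.5 × 48/52 = 137, of which about 69 precede it.

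**Dispersion.** Write variance = μ + kμ². The stated 1.3 can mean variance/mean = 1.3, so k = 0.3/μ: 0.15 at mean 2, or 0.3/1.846 = 0.16 at 2 per year over 48 weeks. It can also mean k = 1/1.3 = 0.77 or k = 1.3. Results are given for k = 0.16, 0.77 and 1.3.

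**Dilution.** Suppose the rate ratio per SD of VDP change is 1.3 in Weeks 24-48 and 1 before. With half the events in each window, the 0-48 log rate ratio is about ½ × ln 1.3 = 0.131, and exp(0.131) = 1.14. Simulation agrees:

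| Model | Median rate ratio | % significant at k = 0.16 / 0.77 / 1.3 |
|---|---|---|
| Weeks 0-48 | 1.14 | 30 / 18 / 16 |
| Weeks 24-48, no early count | 1.30 | 56 / 43 / 33 |

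**Carry-over.** VDP change = b × (early events that still count) + N(0,1), with no effect of VDP change on later events. Both b = 0.3 residual SD per event and its persistence are assumptions. Counts are gamma-Poisson at 2 and 1.3 per 48 weeks; the test is two-sided 5%; there are 1,500 trials per cell (Monte Carlo standard error at most 1.3 points). Entries are % significant at k = 0.16 / 0.77 / 1.3.

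| Shift lasts | Weeks 0-48 model | Landmark, no early count |
|---|---|---|
| 28 days | 9 / 9 / 9 | 5 / 6 / 7 |
| 12 weeks | 19 / 26 / 35 | 5 / 10 / 18 |
| Permanently | 53 / 73 / 82 | 6 / 22 / 42 |

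With no shift at all (b = 0), the 0-48 model gives 5 / 6 / 6. With the early count as a covariate, the landmark stays at about 5-8% throughout. With a permanent shift, b = 0.1 gives 11 / 17 / 23 in the 0-48 model and b = 0.5 gives 87 / 98 / 99.

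A second simulation took the rate per year and the dispersion as known. For a permanent 0.3 SD shift at k = 0.77 and 1.3, it gave 61% and 74% (0-48), 17% and 31% (landmark without count), and 2-4% (with count).

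**Reading the permanent row.** At k = 0.16 almost all of the excess disappears in the landmark (53% against 6%), so it is carry-over. At k = 1.3 the landmark is itself significant in 42%. VDP change then marks patients with a high underlying rate, who do go on to exacerbate. Much of the 82% is therefore real prediction through shared patient risk, not artefact.

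**The case against.** The strongest reply is that the 0-48 model does what it is asked to do. The objective is a relationship, the study is exploratory, and its focus is estimation. The background hopes that "this assessment may offer improved sensitivity compared with an AEx endpoint allowing for shorter duration clinical trials". A 24-week readout that stands in for a 48-week exacerbation endpoint may properly be judged against the whole 48-week rate, early events included. This stands, and it is why the primary model should stay.

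Four stronger readings are tempting, and the documents do not support them.

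- **That the study's prognostic aim is compromised.** Section 2 calls the MRI a prognostic tool, but Section 1.3 ties that word to baseline metrics, which precede every on-study event and have no overlap. The point concerns VDP change only.
- **That a positive primary result would be an artefact.** No text says that exacerbations move VDP. The carry-over figures run from about 9% to 82% according to assumed persistence and dispersion, and the upper end is partly true prediction.
- **That the plan has no landmark.** Section 6.4.1 refers to the SAP for detail and speaks of a minimum and an initial model, so more is foreseen.
- **That the no-signal rule would usually suppress a landmark.** This needs the landmark to sit among the sensitivity analyses and needs a definition of signal, which Section 6.4.1 does not give. Only if signal means two-sided p < 0.05, in the forward-only case with rate ratio 1.3, would 51-60% of significant landmarks accompany a null 0-48 model. A one-sided 5% rule gives 40-51%.

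**Conclusion.** The point holds as a limit on interpretation and does not invalidate the primary analysis. The 50% overlap follows from the plan's own windows. The event counts add only its assumed rates and a constant hazard. The dilution of 1.3 to about 1.14 needs no assumption about exacerbations moving VDP, only that the forward effect is confined to later events. The overstatement is conditional on an unknown shift and can be negligible or large. So the 0-48 estimate can err in either direction as a measure of what VDP change says about later exacerbations, and it cannot carry the word *predict* by itself. Whether the SAP already deals with this cannot be judged from the text available.

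**What to change.** - Keep the 0-48 negative binomial model as the primary estimate, and report its result as *is associated with*.
- Confirm that the SAP has, or add, a landmark negative binomial model: moderate or severe exacerbations from the day after the actual Week 24 scan to Week 48, offset log time at risk, with VDP change and treatment as covariates.
- Report it without the baseline-to-scan exacerbation count (does VDP change predict later events by any route?) and with it (does it add to in-trial history?). The second question matters because Section 1.1 names exacerbation history as the strongest known predictor of risk.
- Run it whatever the primary result, outside the no-signal rule.
- Base any statement that VDP change predicts later exacerbations on these estimates and their confidence intervals, and say which version is meant.

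The change is to wording and programming only; exacerbation dates are already collected (Section 4.5.13). The statistical cost is real. The standard error per SD of VDP change grows by about 15-36% without the early count and 4-36% with it (no shift). If the true rate ratio is 1.3 in both windows, two-sided 5% power is 79% (0-48), 53% (landmark without count) and 43% (with count) at k = 0.16, and 43%, 32% and 14% at k = 1.3. The with-count estimate is then also attenuated, to 1.25 or 1.14, because the early count carries part of the same signal. The landmark is therefore an addition, not a replacement, and a null landmark should be read as imprecise.
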